4. Follow treatment guidelines according to Appendix I. If necessary, deviations from guidelines may occur per discretion of treating physician and consulting physician.
5. 7 investigators at the lead sites have been identified as APL experts.
6. Consent patient after APL diagnosis is confirmed.

Rev. Add2

1. Introduction

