1.3 Study Overview

This is a multi-center study with 7 lead investigators accruing at 6 lead sites: Medical College of Georgia at Augusta University, Augusta, GA; Memorial Sloan Kettering Cancer Center, New York, NY; Mayo Clinic, Rochester, MN; Northwestern University, Chicago, IL; University of Pennsylvania, Philadelphia, PA and Mayo Clinic, Jacksonville, FL. The study will be restricted to the above mentioned **SIX NCTN SITES**. All six sites will be referred to as lead sites. **Other Academic sites will not participate in this trial.**

Rev. Add2

Physicians treating patients at NCORP community centers will call one of the lead investigators as early as possible but no later than 3 days after APL directed treatment is started. The algorithm will be made available and the contacted lead investigator will provide guidance during induction and follow up treatment. The providing physicians will be encouraged to call as and when there are problems.

1.3.1 Treatment guidelines:

The treatment guidelines were developed after extensive review of the literature on standard treatment of APL. Physicians at the NCORP community centers will be provided this algorithm. The study does not exclude patients by age or comorbidities and complete adherence might not be feasible in certain clinical circumstances. This study is directed at co-managing patients by discussions between APL experts and treating physicians to improve the care.

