Appendix I

Acute Promyelocytic Leukemia Treatment Guidelines

Developed at Georgia Regents University, August 2013 Revised May 2017

AUTHORS: [name] [contact] Office: [contact]
[name] [contact] Office: [contact]

WORK-UP

BASELINE

- Chest X-ray
- Echocardiogram and EKG
- PICC line placement – NO central lines in chest or neck or invasive procedures (bronchoscopy, spinal tap, endoscopy)
- Bone marrow examination (aspirate, biopsy, flow, cytogenetics, FISH for t15:17, PCR for PML-RAR α). Day 14 marrow is **NOT** necessary.

DAILY

- CBC, CMP, PT, PTT, fibrinogen **TWICE DAILY** until lab & clinical coagulopathy is resolved. CMP daily and twice a day as dictated by clinical condition.
- D-dimer **ONCE DAILY** for **ENTIRE** hospitalization.

PREVENTION/TREATMENT OF COAGULOPATHY

- Intracranial, pulmonary and GI hemorrhages are frequent
- Risk of hemorrhage is ↑ with the presence of any of the following - active sites of bleeding, ↓ fibrinogen, ↑ D-dimers, ↑ PT & PTT, ↑ WBC, ↑ peripheral blasts, renal failure and poor performance status;

Rev. Add2

- **Keep platelets above 50,000 (until resolution of DIC)**
- If there are any active sites of bleeding on presentation (e.g., needle sticks, bone marrow biopsy sites,), and prolonged PT/PTT), give 4 units of fresh frozen plasma (FFP) at the start of ATRA and chemotherapy. **CONTINUE FFP support TWICE A DAY** until clinical bleeding resolves.

Rev. Add2

- **Keep fibrinogen above 150.** Use 10 units of cryoprecipitate if < 150 (until DIC resolves).
- When clinical & lab coagulopathy is resolved, blood product support is per standard guidelines.

→ APL IS A MEDICAL EMERGENCY - START ATRA ASAP ←

PREVENTION/TREATMENT OF APL DIFFERENTIATION SYNDROME

Differentiation Syndrome-symptoms are – dyspnea, unexplained fever, ↑ weight, peripheral edema, unexplained hypotension, acute renal failure, CHF, pleuro-pericardial effusions, and interstitial pulmonary infiltrates.

- Daily weights - **BEDSIDE SCALES ONLY**
- Keep I/O matched – **METICULOUSLY**

Rev. Add2

- Diuretics if increase in fluid retention or weight.
- Prednisone 0.5 to 1 mg/Kg in all patients for 2 weeks as prophylaxis starting on day 1 followed by a taper.
- Increase Dexamethasone to 10 mg IV BID from the prophylactic dose above, if onset of DS symptoms.
- If WBC > 10,000, dexamethasone 10 mg IV bid could be started on day 1 before initiating ATRA.

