- Temporary discontinuation of ATRA or Arsenic Trioxide (ATO) is indicated only in case of severe cases of DS.
- Continue dexamethasone until 3 days after all symptoms are resolved. ATRA and/or arsenic can be resumed.

SUPPORTIVE CARE

- Allopurinol 300 mg daily.
- Antibiotic prophylaxis - levofloxacin 500 mg po daily or similar antibiotic.
- Antifungal prophylaxis - posaconazole 200 mg po 3 x3x daily, voriconazole 200 mg po 2 x2x daily, Micafungin 50 mg daily or a similar drug as per institutional standard.
- Anti-viral prophylaxis - acyclovir 400 mg po 2 x2x daily or valacyclovir 1000 mg PO daily.
- RBC transfusion recommended when HGB ↓ 8.

INDUCTION OF LOW AND INTERMEDIATE RISK PATIENTS WBC < 10,000 and PLTS < 40,000 -

- ATRA 45mg/m² in divided doses twice a day plus ATO 0.15 kg daily until complete hematologic remission (no anthracycline). Prednisone 0.5 mg/kg for 14 days followed by a gradual taper if no evidence of DS.
OR
- ATRA on Day 1 at 45 mg/m² DAILY in divided doses twice a day until complete hematologic remission.
- Idarubicin 12 mg/m² on Days 2, 4, 6 and 8. Prednisone 0.5 mg/kg for 14 days followed by a gradual taper if no evidence of DS.

Rev. Add2

INDUCTION OF HIGH RISK PATIENTS WBC > 10,000

- ATRA to be started as soon as diagnosis is suspected at 45 mg/m² in divided doses twice a day until complete hematologic remission.
- Idarubicin to be started on the SAME DAY OR AS SOON AS POSSIBLE WHEN THE DIAGNOSIS IS CONFIRMED at 12 mg/M² on days 1, 3, 5 and 7.
- Dexamethasone 10 mg IV bid on days 1 to 14 followed by a taper.
- Arsenic at 0.15 mg/Kg can be started on day 10.
- Even if the genetic results are not available, it is reasonable to start Idarubicin if the diagnosis is otherwise strongly suggested.

Rev. Add2

ARSENIC ADMINISTRATION

- Prednisone 0.5 mg/Kg from days 1-14 days followed by a taper. If high risk, dexamethasone 10 mg IV bid on days 1 to 14 followed by a taper.
- Watch for differentiation syndrome.

- Watch for prolonged QTc interval.
- Keep Mg above 2.0 and K above 4.0.
- Follow LFTs for grade 2 - 4 liver dysfunction. If this occurs HOLD arsenic.

SUGGESTED MANAGEMENT OF ATRA/ARSENIC-INDUCED LEUKOCYTOSIS

- WBC 5 - 50 K- Hydroxyurea 500 mg qid
- WBC > 50K- Hydroxyurea 1000 mg qid
- If leukocytosis does not resolve one or two doses of Idarubicin or Cytarabine could be considered.
- **NO LEUKOPHERESIS.**

ELDERLY PATIENTS / \geq 60 years AND PATIENTS WITH SEVERE COMORBID CONDITIONS

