- May not be candidates for cytotoxic chemotherapy.
- Consider dose reduction of ATRA. Single agent and consider 25 mg/M2 for 14 days.
- Consider dose reduction of ATO and consider 0.075 mg/M2 and add on day 15.

A Simplified Patient Care Strategy to Decrease Early Deaths in Acute Promyelocytic Leukemia (APL)

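### Appendix I gives the reduced arsenic trioxide dose for older or frail patients per m² although the standard dose is per kg, so the printed dose is about 1% of standard

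*Combined protocol and SAP*

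**What the plan says.** Note 4 to the Schema directs sites to the guideline sheet ("Follow treatment guidelines according to Appendix I"), while allowing the treating and consulting physicians to deviate where necessary. Appendix III says that NCORP providers receive the sheet.

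On arsenic, Appendix I has three dose statements:

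- High-risk induction: "Arsenic at 0.15 mg/Kg can be started on day 10".
- Low- and intermediate-risk induction: "plus ATO 0.15 kg daily until complete hematologic remission (no anthracycline". Here the milligram part of the unit is absent.
- Patients aged 60 or over or with severe comorbid conditions: "Consider dose reduction of ATO and consider 0.075 mg/M2 and add on day 15".

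The line just above the last of these reduces ATRA: "Consider dose reduction of ATRA. Single agent and consider 25 mg/M2 for 14 days". The standard ATRA dose on the same sheet is 45 mg/m², so ATRA is dosed by surface area in both places.

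Section 1.3.1 confirms that the patients covered by the reduced-dose block will be enrolled: "The study does not exclude patients by age or comorbidities".

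**The concern.** The reduced ATO figure, 0.075, is exactly half of 0.15. That fits an intended 50% reduction, but the unit attached to it is per m² rather than per kg. Only arsenic changes basis, and it does so directly beneath an ATRA line that ends in the same per-m² unit. Nowhere else does the protocol dose arsenic by surface area or give a reason for doing so.

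This matters because the sheet is part of what is being tested. The primary objective (Section 2.1.1) concerns the simplified guidelines together with expert support. Section 1.2 singles out older patients: seven of the ten deaths in the pilot experience were in the elderly. The same block of Appendix I warns that these patients may be unsuitable for cytotoxic chemotherapy and suggests reduced single-agent ATRA for 14 days. Arsenic from day 15 is then the only other antileukemic drug the block offers. Followed literally, the line gives almost none of it. Section 1.3.2 adds that some centers may see too few APL patients to be proficient, and those are the readers the sheet is meant to help. Section 7.3.2 also scores compliance with the guidelines as a yes/no outcome, so the guideline should state a usable dose.

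**Working it through.** The protocol gives no derivation of the reduced dose, so there is no figure of its own to reproduce. The check is unit arithmetic.

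**Inputs from Appendix I.** Standard ATO 0.15 mg/kg; reduced ATO as printed 0.075 mg/m²; standard ATRA 45 mg/m²; reduced ATRA 25 mg/m².

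**Inputs assumed.** The documents give no body size. The reference patient is 70 kg and 1.8 m². The range uses 50 kg with 1.5 m² and 110 kg with 2.3 m².

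**Formulas.**

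- Standard dose = 0.15 × weight
- Half dose on the weight basis = 0.075 × weight
- Printed dose = 0.075 × surface area
- Effect of the unit alone = (0.075 × weight) / (0.075 × surface area) = weight / surface area

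**Results.**

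| Assumed patient | Standard (mg) | 0.075 mg/kg (mg) | Printed (mg) | Unit effect | Printed as share of standard |
|---|---|---|---|---|---|
| 50 kg, 1.5 m² | 7.5 | 3.75 | 0.1125 | 3.75 / 0.1125 = 33.3 | 0.1125 / 7.5 = 1.50% |
| 70 kg, 1.8 m² | 10.5 | 5.25 | 0.135 | 5.25 / 0.135 = 38.9 | 0.135 / 10.5 = 1.29% |
| 110 kg, 2.3 m² | 16.5 | 8.25 | 0.1725 | 8.25 / 0.1725 = 47.8 | 0.1725 / 16.5 = 1.05% |

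A second calculation took surface area from height and weight as √(kg × cm / 3600). It gave a unit effect of 32.9 at 45 kg and 150 cm, and 48.3 at 120 kg and 185 cm. The order of magnitude does not depend on the body size chosen.

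**Comparison with the neighbouring line.** The ATRA reduction keeps 25 / 45 = 55.6% of its standard dose. An ATO dose of 0.075 mg/kg would keep 0.075 / 0.15 = 50%. The printed ATO line keeps about 1%.

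**Could another reading rescue the line?** The rest of the protocol was checked for a per-m² arsenic dose, an explanation of the change of basis, or a correction. There is none.

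**The case against.** The mismatch and the arithmetic are not in dispute. The case on the other side has four parts.

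*The intended dose is not stated.* The 39-fold figure compares the printed dose with 0.075 mg/kg, which appears nowhere in the protocol, and it uses an assumed body size. Section 1.2 says the approach to older patients resembles published Chinese experience, which the documents do not reproduce. This stands, and it is why the intended dose must be confirmed before the text is changed. The comparison with the standard dose needs no such inference: at any adult size the printed line is between 1.0% and 1.5% of it.

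*The text may have been damaged in conversion from PDF.* The missing milligram unit in the low- and intermediate-risk branch could well be a lost string, so it is not counted here as an error. The same sheet shows other conversion damage. Checking both lines against the PDF is reasonable. However, turning a per-kg unit into a per-m² unit is a much less likely conversion fault than dropping characters, and the sheet otherwise keeps the two units distinct.

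*Harm is unlikely.* The line only asks the physician to consider the dose, and it applies from day 15. Expert contact is required within 3 days of starting therapy, and communication should continue until remission (Section 5.2.1). Experts are available around the clock (Appendix III), deviations are allowed, and 0.135 mg is so far out of range that a pharmacist would probably query it. All of this lowers the risk, but each safeguard relies on someone noticing. Calls after the first are made as needed; they are not required for each dose.

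*It is only a wording slip with no statistical consequence.* No effect on the primary endpoint, sample size or power is claimed. But this is a dose on the sheet that defines the intervention, and a slip there bears on patient safety in a way that one in background text would not.

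**Conclusion.** The concern holds. The reduced ATO line in Appendix I is wrong as written: its dosing basis changes from weight to surface area without explanation, giving a dose of about 1.3% of standard in the reference patient. If 0.075 mg/kg was meant, the printed dose is about 39 times too low, with a range of about 33 to 48. Those multiples rest on the assumed body sizes and on the inference that a 50% reduction was intended; the finding that the printed dose is close to zero relative to standard rests on the body sizes alone.

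This should be fixed, but the safeguards already in the protocol make it less than urgent.

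Two smaller wording points on the same sheet do not bear on this conclusion:

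- The heading "INDUCTION OF LOW AND INTERMEDIATE RISK PATIENTS WBC < 10,000 and PLTS < 40,000" does not numerically cover patients with a low white count and platelets of 40,000 or more, or a white count of exactly 10,000, although its label shows where they belong.
- The line "Increase Dexamethasone to 10 mg IV BID from the prophylactic dose above, if onset of DS symptoms" refers back to a prophylactic dose that is prednisone, although the target dose is clear.

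**What to change.** Have the study chair and a pharmacist confirm the intended reduced ATO dose. Then restate it in mg/kg daily, on the same basis as the standard dose. At the same time, check the ATO unit in the low- and intermediate-risk branch against the PDF, and correct it to mg/kg if the milligram part is missing there too. Reissue Appendix I to all sites.

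The same reissue can tidy the two minor points: define the low- and intermediate-risk branch by a white count of 10,000 or less whatever the platelet count, and word the differentiation-syndrome line as a switch to dexamethasone 10 mg IV twice daily at onset of symptoms.

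The cost is a short administrative amendment and redistribution of the sheet. Nothing in the design, sample size or analysis changes.

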Appendix II

APL Expert and NCORP Provider Communication

1. Date patient admitted -
2. Date APL suspected -
3. Date APL confirmed -
4. Date APL therapy started -
5. Date APL expert contacted -
6. Subsequent communications -

Date:

Date:

Date:

Date:

Date:

Date:

Date:

Date:

Date:

A Simplified Patient Care Strategy to Decrease Early Deaths in Acute Promyelocytic Leukemia (APL)

Appendix III

NCORP PROVIDER INFORMATION SHEET

This is a research study focused on decreasing induction mortality in Acute Promyelocytic Leukemia (APL). Historical data shows an induction mortality of 30% in the general population and the purpose of this study is to decrease it to < 15%. NCORP providers will be given this information sheet along with the treatment guidelines in Appendix I.

- A. The study will consist of using the simplified APL treatment algorithm that is attached.
- B. Equally important is for the provider at NCORP sites to call an APL expert listed in the protocol or the PI/Co-PI. Cell phone numbers of APL experts are in the Protocol.
- C. The APL expert will function as a resource during induction to prevent and manage complications. It is suggested that the provider at NCORP sites call the APL expert as frequently as needed during the first 4 weeks. The experts are available 24/7.
- D. NCORP providers will document discussion with the APL expert and clinical decisions in the Medical Record. APL experts will fill the Expert/NCORP Provider communication sheet.
- E. There are no obvious discomforts to the patient since the patient will be treated on the accepted standard of care. Expert support may help in preventing and managing complications and improving outcome.
- F. We will retain all patient records and signed informed consent forms filed in a secure location. Database is maintained using web-based database system. Only research members are granted access to web-based database system with user ID and password.
- G. Participation is voluntary and the patient may choose not to participate in the trial. In that case the patient will be treated per usual treatment guidelines. Participants may discontinue at any time without penalty or loss of benefits.

A Simplified Patient Care Strategy to Decrease Early Deaths in Acute Promyelocytic Leukemia (APL)

